#### 8.2.2.4 Dermatology Life Quality Index (DLQI)

The DLQI is a subject-reported quality of life index which consists of 10 questions concerning symptoms and feelings, daily activities, leisure, work, school, personal relationships, and treatment during the last week. Each question is scored on a scale of 0 to 3 where 0="not at all", 1="a little", 2="a lot", or 3="very much". The scores are summed, giving a range from 0 (no impairment of life quality) to 30 (maximum impairment). Question 7 includes 2 questions, if the subject answers 'Yes' to Q7, the score given is a 3. If the subject answers 'No' to Q7, they are asked the second question where a score of 0='not at all', 1='a little', or 2='a lot' is given. Certain questions include an option for not relevant. When scoring, any questions deemed 'not relevant' will take on a value of 0.

[figure not shown]
. Interpretation of DLQI scores is as follows:

- 0-1 = no effect at all on patient's life
- 2-5 = small effect on patient's life
- 6-10 = moderate effect on patient's life
- 11-20 = very large effect on patient's life
- 21-30 = extremely large effect on patient's life

Sponsor: Bristol-Myers Squibb

Protocol no: IM011046

Individual scores for each question will be provided by the eCOA system. The DLQI score will be derived in the analysis datasets.

Sponsor: Bristol-Myers Squibb  
Protocol no: IM011046

#### 8.2.2.11 Psoriatic Arthritis Screening and Evaluation (PASE) Questionnaire

The PASE questionnaire will be administered at Screening in subjects with peripheral joint complaints. The PASE questionnaire is a self-administered tool that is used to screen for psoriatic arthritis among subjects who have psoriasis. The PASE questionnaire consists of 15 questions subdivided into 7 questions focusing on symptoms of psoriatic arthritis, and 8 questions focusing on the impact of psoriatic arthritis on function. Each question is scored on a 1 to 5 scale, with a maximum symptom sub-scale score of 35, a maximum function sub-scale score of 40 giving a total maximum score of 75. A score of 47 or above has been shown to distinguish between psoriatic arthritis and non-psoriatic arthritis. This questionnaire is only intended to be a screening tool for psoriatic arthritis and does not replace a comprehensive musculoskeletal exam performed by a rheumatologist. This information will not be summarized.

Sponsor: Bristol-Myers Squibb

Protocol no: IM011046

Individual score to each of the 15 questions will be collected in the eCOA system. The sub-scale scores and total score will be derived in the analysis datasets.

#### 8.2.2.12 Eight-Item Patient Health Questionnaire (PHQ-8)

The PHQ-8 is established as a valid diagnostic and severity measure for depressive disorders in large clinical studies. Each of the 8 questions is based on a 2-week recall and scored on a scale of 0 to 3 by a tick box as: 0=Not at All, 1=Several Days, 2=More than Half the Days, and 3=Nearly Every Day. A PHQ-8 score is derived by summing the scores for the 8 questions. The total PHQ-8 score ranges from 0-24. Scoring interpretation is as follows:

- 0-4 = no significant depressive symptoms
- 5-9 = mild depressive symptoms
- 10-14 = moderate depressive symptoms
- 15-19 = moderately severe depressive symptoms
- 20-24 = severe depressive symptoms

Response to each individual question is collected in the eCOA system. The total score will be derived in the analysis datasets.

#### 8.2.2.13 electronic Columbia-Suicide Severity Rating Scale (eC-SSRS)

The electronic Columbia-Suicide Severity Rating Scale (eC-SSRS) is a computer-automated, patient-reported version of the C-SSRS instrument that defines 11 categories of suicidal ideation and behavior (SIB) events. Categories and definitions are provided in Appendix 23 of the protocol. The categories are as follows:

- Suicidal ideation
  1. Wish to be dead
  2. Non-specific active suicidal thoughts
  3. Active suicidal ideation with any methods without intent to act
  4. Active suicidal ideation with some intent to act, without specific plan
  5. Active suicidal ideation with specific plan and intent
- Suicidal behavior
  1. Preparatory acts or behavior
  2. Aborted attempt
  3. Interrupted attempt
  4. Actual attempt (Non-fatal)
  5. Completed suicide
- Self-injurious behavior, no suicidal intent

### 8.3 Missing, Unknown, or Partial Dates

Start Date		Stop Date						
		Complete: yyyymmdd		Partial: yyyyymm		Partial: yyyy		Missing/ Ongoing
<1 st dose	≥1 st dose	<1 st dose yyyymm	≥1 st dose yyyymm	<1 st dose yyyy	≥1 st dose yyyy			
Partial: yyyymm	= 1 st dose yyyymm	2	1	n/a	1	n/a	1	1
	≠ 1 st dose yyyymm		2	2	2	2	2	2
Partial: yyyy	= 1 st dose yyyy	3	1	3	1	n/a	1	1

Sponsor: Bristol-Myers Squibb

Protocol no: IM011046

	≠ 1 st dose yyyy		3		3	3	3	3
Missing		4	1	4	1	4	1	1

1 = Impute as the date of first dose

2 = Impute as the first of the month

3 = Impute as January 1 of the year

4 = Impute as January 1 of the stop year

Note: If the start date imputation leads to a start date that is after the stop date, then there is a data error and the start date is not imputed.

Imputation rules for partial or missing stop dates:

1. Initial imputation
  - a. For partial stop date "mmyyyy", impute the last of the month.
  - b. For partial stop date "yyyy", impute December 31 of the year.
  - c. For completely missing stop date, do not impute.
2. If the stop date imputation leads to a stop date that is after the death date, then impute the stop date as the death date.
3. If the stop date imputation leads to a stop date that is before the start date, then there is a data error and the stop date is not imputed.

Imputation rules for partial or missing death dates:

1. If death year and month are available but day is missing:
  - a. If "mmyyyy" for last contact date = "mmyyyy" for death date, set death date to the day after the last contact date.
  - b. If "mmyyyy" for last contact date < "mmyyyy" for death date, set death date to the first day of the death month.
  - c. If "mmyyyy" for last contact date > "mmyyyy" for death date, data error and do not impute.

If both month and day are missing for death date or a death date is totally missing, set death date to the day after the last contact date.

## 8.4 Study Periods

Period 1 = Week 0 to Week 16 visit date

Period 2 = Week 16 visit date +1 to Week 24 visit date

Period 3 = Week 24 visit date +1 to Week 52 visit date

Follow-up = 4 week follow-up period

## 8.5 Day Ranges for Analysis Visits

Below are the day ranges for the analysis visit definitions. If more than one visit occurs within an analysis visit, then the visit that is closest to the target date should be used for analysis.

Period	Week	Target Day	Day Range
Baseline			Screening, 1
Period 1			
Week 1		8	2, 11
Week 2		15	12, 18
Week 4		29	19, 43
Week 8		57	44, 71
Week 12		85	72, 99
Week 16		113	100, 127 (or Week 16 drug dispense date)
Period 2			
Week 20		141	1 st day after Week 16 drug dispense date, 155

Sponsor: Bristol-Myers Squibb

Protocol no: IM011046

Period			
Week	Target Day	Day Range	
Week 24	169	156, 183 (or Week 24 drug dispense date)	
Period 3			
Week 28	197	1 st day after Week 24 drug dispense date, 211	
Week 32	225	212, 239	
Week 36	253	240, 267	
Week 40	281	268, 295	
Week 44	309	296, 323	
Week 48	337	324, 351	
Week 52	365	352, last visit date prior to Safety Follow-up	
Safety Follow-up	393	Safety Follow-up visit	

Sponsor: Bristol-Myers Squibb  
Protocol no: IM011046

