**Table 2: On Treatment Procedural Outline (IM011046): Week 0 through Week 20**

Procedure	Week 0 Baseline/D1 V2	Week 1 D8 (±3 d) V3	Week 2 D15 (±3 d) V4	Week 4 D29 (±3 d) V5	Week 8 D57 (±3 d) V6	Week 12 D85 (±3 d) V7	Week 16 D113 (±3 d) V8	Week 20 D141 (±3 d) V9	Notes
Clinical Efficacy/Health Outcomes									
DLQI	X	X	X	X	X	X	X	X	
sPGA	X	X	X	X	X	X	X	X	
PASI	X	X	X	X	X	X	X	X	
ss-PGA a	X	X	X	X	X	X	X	X	

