##### **9.4.2.1 Imputation Methods for Secondary Endpoints**

[figure not shown]
The NRI will be applied to the analyses of binary secondary efficacy endpoints for subjects who discontinue early, start a protocol prohibited medication/therapy that could improve psoriasis, or who have otherwise missing endpoint data prior to the specified timepoint.

For continuous secondary efficacy endpoints, a modified baseline observation carried forward (mBOCF) will be used for missing data. The baseline observation will be carried forward for subjects who discontinue study treatment due to:

- Lack of efficacy
- AEs

and for subjects who start a protocol prohibited medication/therapy that could improve psoriasis prior to the endpoint. The last valid observation will be carried forward for all other subjects with missing data.

At Week 24, subjects originally randomized to apremilast 30 mg BID who do not achieve PASI 50 response will be switched in a blinded manner to BMS-986165 6 mg QD. These subjects will be considered nonresponders to apremilast for the timepoints after the switch for the binary endpoints for the Week 52 comparisons. The mBOCF described above will be used for the continuous endpoints. Subjects will be analyzed according to their original randomized treatment group.

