# 8.0 Conventions

## 8.1 General Definitions

The following data definitions and handling conventions will be used for general analysis:

Term	Definition
Study Day	Study day is calculated as: assessment date – date of first dose + 1
Baseline	Unless otherwise stated, Baseline is defined as the measurement at the randomization visit (Week 0). If the measurement at the randomization visit is missing, then a prior measurement during the screening period may be used as baseline. Baseline assessments must be performed per protocol and standard of care assessments may not be used for baseline. Baseline for each PSSD question will be calculated as the average value over the 7 days prior to the randomization visit. In the event of missing values in the 7 days prior to the randomization visit, daily

Sponsor: Bristol-Myers Squibb  
Protocol no: IM011046

	scores from at least 4 days out of the 7 days can be used to calculate the average score. If > 3 daily scores in the last 7 days are missing for a particular question, then the baseline value for that question will be missing. If any questions are missing baseline after using the described rule, then the baseline value for the subscore using that question and the baseline value for the total score will be missing.
Change from Baseline	Change from baseline is defined as (value at post-baseline visit – value at baseline).
Change in the maximum post-baseline value or change in the worst post-baseline value	Change from baseline in the maximum post-baseline value is defined as highest observed value or grade post-baseline. The change is calculated using this value as the post-baseline value.  Change from baseline in the worst post-baseline value is defined as worst observed value post-baseline. The change is calculated using this value as the post-baseline value.
Concomitant and Prior Medication	Prior medications are defined as medications with a stop date prior to the first dose of study treatment. Concomitant medications are defined as any medications ongoing at the start of study treatment or with a start date on or after the first dose date.
End of Study (EOS) Date	The EOS date is the date recorded on the eCRF that a randomized subject either discontinued or completed the study. If the subject is lost to follow-up, the EOS date will be the date of the last visit assessment obtained.

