## Appendix 2 Summary of Efficacy Assessments

Assessment	Outcome Measure	Endpoint	Comparison	Analyses
sPGA (Sec 8.2.1.1)	sPGA 0/1 with at least 2 point improvement from baseline	W16	BMS vs. PBO	CMH, sensitivity analyses including tipping point analysis, multiple imputation (Sec 6.1.1-3)
			BMS vs. apremilast	CMH (Sec 6.1.2.1)
		W24/52	BMS vs. apremilast	CMH (Sec 6.1.2.1)
	sPGA 0	Baseline->W16 over time	BMS vs. PBO	Binary GEE & CMH by Week (Sec 6.1.5.1)
			BMS vs. apremilast	Binary GEE & CMH by Week (Sec 6.1.5.1)
		W16	BMS vs. PBO	CMH (Sec 6.1.2.1)
			BMS vs. apremilast	CMH (Sec 6.1.2.1)
		Baseline->W16 over time	BMS vs. PBO	Binary GEE & CMH by Week (Sec 6.1.5.1)
PASI (Sec 8.2.1.2)	PASI 75	W16	BMS vs. PBO	CMH, sensitivity analyses including tipping point analysis, multiple imputation (Sec 6.1.1-3)
			BMS vs. apremilast	CMH (Sec 6.1.2.1)
	W24/52		BMS vs. apremilast	CMH (Sec 6.1.2.1)

Sponsor: Bristol-Myers Squibb  
Protocol no: IM011046

Assessment	Outcome Measure	Endpoint	Comparison	Analyses
PASI 90		Baseline->Week 16 over time	BMS vs. PBO	Binary GEE & CMH by Week (Sec 6.1.5.1)
		Baseline->Week 52 over time	BMS vs. apremilast	Binary GEE & CMH by Week (Sec 6.1.5.1)
	W16		BMS vs. PBO	CMH (Sec 6.1.2.1)
			BMS vs. apremilast	CMH (Sec 6.1.2.1)
		W52	BMS vs. apremilast	CMH (Sec 6.1.2.1)
		Baseline->W16 over time	BMS vs. PBO	Binary GEE & CMH by Week (Sec 6.1.5.1)
	PASI 100	Baseline->W52 over time	BMS vs. apremilast	Binary GEE & CMH by Week (Sec 6.1.5.1)
		W16	BMS vs. PBO	CMH (Sec 6.1.2.1)
			BMS vs. apremilast	CMH (Sec 6.1.2.1)
		Baseline->W16 over time	BMS vs. PBO	Binary GEE & CMH by Week (Sec 6.1.5.1)
		Baseline->W52 over time	BMS vs. apremilast	Binary GEE & CMH by Week (Sec 6.1.5.1)

Sponsor: Bristol-Myers Squibb  
Protocol no: IM011046

Assessment	Outcome Measure	Endpoint	Comparison	Analyses
ss-PGA (Sec 8.2.1.4)	ss-PGA 0/1 among subjects with a baseline ss-PGA $\geq 3$	W16	BMS vs. PBO	CMH (Sec 6.1.2.1)
			BMS vs. apremilast	CMH (Sec 6.1.2.1)
		Baseline->W16 over time	BMS vs. PBO	Binary GEE & CMH by Week (Sec 6.1.5.1)
PGA-F (Sec 8.2.1.6)	PGA-F 0/1 among subjects with a baseline PGA-F score $\geq 3$	W16	BMS vs. PBO	CMH (Sec 6.1.2.1)
		Baseline->W16 over time	BMS vs. PBO	Binary GEE & CMH by Week (Sec 6.1.5.1)
pp-PGA (Sec 8.2.1.8)		W16	BMS vs. PBO	CMH (Sec 6.1.2.1)
		Baseline->W16 over time	BMS vs. PBO	CMH by Week (Sec 6.1.5.1)

Sponsor: Bristol-Myers Squibb  
Protocol no: IM011046

Assessment	Outcome Measure	Endpoint	Comparison	Analyses

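### SAP 8.5 ends the Week 2 analysis window at Day 18, not at the Day 22 midpoint that its other boundaries imply, so a Week 2 visit on Days 19-22 is labelled Week 4 and leaves Week 2 empty

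*SAP*

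**What the plan says.** SAP 8.5 lists a target day and a day range for each analysis visit. Week 2 has target Day 15 and range 12 to 18; Week 4 has target Day 29 and range 19 to 43. The section then adds one selection rule for the case where several visits share a range: "then the visit that is closest to the target date should be used for analysis". Days are counted from first dose (SAP 8.1: "assessment date – date of first dose + 1"). At Weeks 16 and 24 the day of drug dispensing can also close the window.

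Protocol Table 2 schedules the two visits as "Week 2 D15 (±3 d) V4" and "Week 4 D29 (±3 d) V5", that is, Days 12-18 and Days 26-32. At Week 2 it calls for sPGA, PASI, DLQI and ss-PGA, as well as vital signs, hematology, chemistry and hs-CRP.

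Superiority to placebo over the first 16 weeks is a secondary objective (SAP 3.2). SAP Appendix 2 gives the by-visit analysis for most of the binary measures as "Binary GEE & CMH by Week (Sec 6.1.5.1").

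**The concern.** Analysis windows exist mainly to place visits that missed their scheduled window. The usual way is to give each day to the nearer target, and the SAP table does that at every boundary between adjacent scheduled visits except this one. Here, three days that lie nearer the Week 2 target are given to Week 4.

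A subject seen a few days late for Week 2 then has no Week 2 value although the assessments were done. Depending on when Week 4 was attended, those assessments either disappear from the by-visit analysis or are reported as Week 4 results 7 to 10 days before the Week 4 target. At stake are the early part of the response curve against placebo and the Week 2 and Week 4 laboratory and vital sign summaries.

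**Working it through.** **Inputs.** Target days and ranges are from SAP 8.5, and protocol visit windows from Protocol Table 2.

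**Step 1: recover the pattern in the table.** For adjacent targets a and b, compute (a + b)/2, round down, and compare with the stated last day of the earlier window.

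| Boundary | Targets | Midpoint | Stated last day |
|---|---|---|---|
| Week 1/2 | 8, 15 | 11.5 → 11 | 11 |
| **Week 2/4** | **15, 29** | **22** | **18** |
| Week 4/8 | 29, 57 | 43 | 43 |
| Week 8/12 | 57, 85 | 71 | 71 |
| Week 12/16 | 85, 113 | 99 | 99 |
| Week 16/20 | 113, 141 | 127 | 127 (or dispense date) |
| Week 20/24 | 141, 169 | 155 | 155 |
| Week 24/28 | 169, 197 | 183 | 183 (or dispense date) |

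From Week 28 to Week 52 the targets are 28 days apart. The six midpoints are 211, 239, 267, 295, 323 and 351, all as stated. So 13 of 14 boundaries agree, and Week 2/4 is 22 − 18 = 4 days early. Where the midpoint is a whole day (Day 43, for example), that day goes to the earlier visit.

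**Step 2: the days affected.**

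| Study day | Days from Day 15 | Days from Day 29 | Stated label | Label under midpoint pattern |
|---|---|---|---|---|
| 19 | 4 | 10 | Week 4 | Week 2 |
| 20 | 5 | 9 | Week 4 | Week 2 |
| 21 | 6 | 8 | Week 4 | Week 2 |
| 22 | 7 | 7 | Week 4 | Week 2 (tie, to the earlier visit) |

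**Step 3: what happens to the late visit.** Under the selection rule, the Day 19-22 visit competes with the real Week 4 visit on distance from Day 29.

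- Week 4 on schedule (Days 26-32): it is at most 3 days from target, while the late Week 2 visit is at least 7. The late visit loses in all 4 × 7 = 28 day pairs and is dropped.
- Week 4 on any of Days 23-43: 4 × 21 = 84 pairs. The late Week 2 visit is dropped in 16 + 15 + 14 + 13 = 58. In 4 pairs the two are equally distant, and 8.5 states no tie-break. In 4 + 5 + 6 + 7 = 22 the late Week 2 visit displaces the real Week 4 visit (for example, Day 22 against Day 37).
- Week 4 missed: the late Week 2 visit is analysed as Week 4.

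These are counts of possible day pairs, not probabilities. In every case Week 2 has no value.

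**Step 4: number of subjects.** The documents give no rate of late visits. Assuming 1% to 5% of 600 subjects attend Week 2 on Days 19-22, 0.01 × 600 = 6 and 0.05 × 600 = 30.

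**The case against.** The best defence is that nothing has been miscalculated. The SAP writes down no midpoint rule; the pattern is inferred from the table. The ranges are contiguous, and the closest-to-target rule chooses among visits already inside one window, so it does not fix where windows end. A reader might infer that 8.5 breaks its own written rule; the text does not support that.

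Day 18 may also be deliberate. It is the end of the protocol's Week 2 visit window, Week 1's last day (11 = 8 + 3) likewise equals its protocol limit, and the titration kit in Protocol 6.1.1 runs 18 days. A symmetric ±3-day window for an early time point is defensible. SAP section 10.0 records edits to the 8.5 table at Weeks 16 and 24 and none to this row.

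Much of this stands. Only visits already outside the protocol window are affected, and the cut cannot be called a proven slip. But the SAP offers none of these reasons, and Week 1's Day 11 fits the midpoint pattern equally well. A strict ±3 window for Week 2 would also not explain why Days 19-21 go to the target further away. Later windows are not held to ±3: Week 8 runs from 13 days before its target to 14 after.

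Two other stronger readings should be resisted. One is that every late Week 2 visit is thrown away; that depends on the Week 4 visit, as Step 3 shows. The other is that observed responders will certainly be analysed as failures. Protocol 9.4.2.1 does apply nonresponder imputation to binary secondary endpoints for subjects "who have otherwise missing endpoint data prior to the specified timepoint", and under that general rule an empty Week 2 would count as nonresponse. The visible SAP imputation rules, however, cover Weeks 16, 24 and 52. SAP 6.1.5.1, which governs the by-week analyses, is not in the text available, so this cannot be confirmed.

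**Conclusion.** The point holds as a small, unexplained inconsistency in one table. One of 14 boundaries departs from the pattern by 4 days, and a Week 2 visit on Days 19-22 leaves Week 2 empty.

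Its reach is limited to by-visit efficacy analyses and by-time-point safety summaries at Weeks 2 and 4, and to the earlier-visit data that feed the multiple imputation in SAP 6.1.1.2. The worst-grade and shift tables in SAP 6.2.3 run through Week 16 and do not turn on a Week 2 or Week 4 label. A reader might infer a threat to the main results, but the coprimary NRI analysis and the key secondary tests are at Weeks 16, 24 and 52 and are unaffected.

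The boundary arithmetic rests on the SAP's own figures. The 6 to 30 subjects rest wholly on the assumed 1-5%, and counting them as nonresponders at Week 2 rests on the protocol's general rule.

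**What to change.** In SAP 8.5, set Week 2 to Days 12-22 and Week 4 to Days 23-43. Days 19-21 then go to the nearer target, and Day 22 follows the tie convention seen elsewhere in the table. If the Day 18 limit is intended, the SAP should say so and explain why Days 19-21 belong to Week 4.

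The cost is two changed ranges in one table, with no new data and no effect on the coprimary NRI analysis or the key secondary tests. The Week 2 window becomes asymmetric (3 days before target, 7 after), which is what unequal visit spacing produces under the midpoint pattern.

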## 10.0 Document History

Version Number	Version Date	Summary of Changes
1.0 - Original Document	09-Jun-2019	Not applicable
2.0 – Amendment 01	30-Sep-2020	Revisions provided below.

**Revisions for Amendment 01:** In addition to the revisions specified below, there were some minor typographical and formatting changes made. Additions are noted by bold text. Removals are noted by strikethrough.

SAP Section	Revised Text	Rationale for Change
2.1 Study Design	
Week 16 activities
 
The coprimary endpoints, static Physician Global Assessment (sPGA) 0/1 and Psoriasis Area and Severity Index (PASI) 75 will be assessed at Week 16. Subjects receiving placebo will be switched in a blinded manner to BMS-986165 6 mg QD at Week 16. Subjects who are randomized to BMS-986165 6 mg QD or apremilast will continue on their assigned treatment regimen in a blinded manner.
	Minor edit to clarify subjects continue on assigned treatment in a blinded fashion.
2.4 Unblinding Information	
No other unblinding <del>prior to study completion and database lock</del> is planned.
 
Additionally, bioanalytical scientists involved in the processing of bioanalytical samples will be unblinded to randomized treatment assignments to minimize unnecessary sample bioanalysis of subjects who are on placebo.
	Added clarification that bioanalytical staff will be unblinded to facilitate bioanalytical sample processing.
2.5 Changes in Statistical Considerations from the Protocol	
<del>There are no changes in statistical considerations from the protocol at this time. The following is a list of the important changes in the SAP from the Statistical Considerations section in the protocol:</del>
 

The hierarchical testing order for the key secondary endpoints has been updated and two separate hierarchies have been provided, one for US submission and one for ex-US submission (see Tables 1 and 2 in Sec. 6.1.3). The hierarchies presented here supersede the one that is in the protocol.

Key secondary endpoints were added for the comparison of BMS-986165 to apremilast for sPGA 0/1, PASI 75, and PASI 90 at Week 24.

Imputation methods were updated to remove the prohibited medication/therapy criteria for binary and continuous endpoints.

	The definition for the Full Analysis Set was modified to include all randomized subjects as this is more representative of the ITT population. Noted that the relevant deviation list was updated from the list in the protocol.

Sponsor: Bristol-Myers Squibb

Protocol no: IM011046

	
 
The Full Analysis Set was changed from “all subjects who were randomized to receive assigned study treatment” in the protocol to “all subjects who are randomized”.
 
The list of relevant protocol deviations provided in the protocol was updated for determination of the Per Protocol population.
 
Logistic regression analyses for binary endpoints were removed as these are similar to the CMH analyses.
 
	
Additional Week 24 endpoints were added.
 
Imputation methods were updated to remove prohibited medication/therapy criteria.
 
Hierarchical testing order of key secondary endpoints were updated and accounting of regional regulatory needs.
 
Removed logistic regression analyses.


4.1.2 Secondary Endpoints
 
4.1.2.1 Key Secondary Endpoints for Comparisons to Placebo
	
The key secondary efficacy endpoints for BMS-986165 compared to placebo at Week 16 are defined as:
 
 
PASI 90 response assessed as a proportion of subjects who achieve a 90% improvement from baseline in PASI score
 
sPGA 0 response assessed as a proportion of subjects with an sPGA score of 0
 
Scalp specific Physician's Global Assessment (ss-PGA) 0/1 assessed as a proportion of subjects with a ss-PGA score of 0 or 1 with at least a 2-point improvement from baseline among subjects with a baseline ss-PGA score <math>\geq 3</math>
 
PSSD symptom score of 0 assessed as a proportion of subjects with a PSSD symptom score of 0 among subjects with a baseline PSSD symptom score <math>\geq 1</math>
 
PASI 100 response assessed as a proportion of subjects who achieve a 100% improvement from baseline in PASI score
 
Physician Global Assessment-Fingernails (PGA-F) 0/1 assessed as a proportion of subjects with a PGA-F score of 0 or 1 with at least a 2-point improvement from baseline among subjects with a baseline PGA-F score <math>\geq 3</math>
 
<del>Change from baseline in Psoriasis Symptoms and Signs Diary (PSSD) symptom score</del>
 
	Updated key secondary endpoints compared to placebo and re-ordered.

Sponsor: Bristol-Myers Squibb

Protocol no: IM011046

	
 
DLQI 0/1 assessed as a proportion of subjects with a DLQI score of 0 or 1 among subjects with a baseline DLQI score <math>\geq 2</math> (Ex-US submission only)
 
<del>Palmoplantar Physician's Global Assessment (pp-PGA) 0/1 assessed as a proportion of subjects with a pp-PGA score of 0 or 1 with at least a 2-point improvement from baseline among subjects with a baseline pp-PGA score <math>\geq 3</math></del>
 
	
4.1.2.2 Key Secondary Endpoints for Comparisons to Apremilast	
The key secondary endpoints for BMS-986165 compared to apremilast at Week 16 are defined as:
 
 
sPGA 0/1 response assessed as a proportion of subjects with an sPGA score of 0 or 1 with at least a 2-point improvement from baseline
 
PASI 75 response assessed as a proportion of subjects who achieve a 75% improvement from baseline in the PASI score
 
PASI 90 response assessed as a proportion of subjects who achieve a 90% improvement from baseline in the PASI score
 
Change from baseline in PSSD symptom score
 
ss-PGA 0/1 assessed as a proportion of subjects with a ss-PGA score of 0 or 1 with at least a 2-point improvement from baseline among subjects with a baseline ss-PGA score <math>\geq 3</math>
 
<del>PASI 100 response assessed as a proportion of subjects who achieve a 100% improvement from baseline in the PASI score</del>
 
sPGA 0 response assessed as a proportion of subjects with an sPGA score of 0
 
PSSD symptom score of 0 assessed as a proportion of subjects with a PSSD symptom score of 0 among subjects with a baseline PSSD symptom score <math>\geq 1</math>
 
 
The key secondary endpoints for BMS-986165 compared to apremilast at Week 24 are defined as:
 
 
sPGA 0/1 response assessed as a proportion of subjects with an sPGA score of 0 or 1 with at least a 2-point improvement from baseline at Week 24
 
PASI 75 response assessed as a proportion of subjects who achieve a 75% improvement from baseline in the PASI score at Week 24
 
PASI 90 response assessed as a proportion of subjects who achieve a 90% improvement from baseline in the PASI score at Week 24
 
 
The key secondary endpoints for BMS-986165 compared to apremilast through Week 52 are defined as:
 
 
sPGA 0/1 response assessed as a proportion of subjects with an sPGA score of 0 or 1 with at least a 2-point improvement from baseline at Week 52 and at Week 24
 
	
Updated key secondary endpoints compared to apremilast and re-ordered.
 
Added some clarifying language.

Sponsor: Bristol-Myers Squibb

Protocol no: IM011046

	

• PASI 75 response assessed as a proportion of subjects who achieve a 75% improvement from baseline in the PASI score at Week 52 and at Week 24

• PASI 90 response assessed as a proportion of subjects who achieve a 90% improvement from baseline in the PASI score at Week 52 and at Week 24

	
4.2 Safety	

• Treatment-emergent adverse events (TEAEs) – defined as:

◦ New nonserious AEs which first occur after the first dose of study treatment through 30 days 4 weeks after the final dose of the study treatment or subject's participation in the study if the last scheduled visit occurs at a later time; New serious adverse events (SAEs) which first occur after the first dose of study treatment through 4 weeks after the final dose of the study treatment or subject's participation in the study if the last scheduled visit occurs at a later time;

◦ SAEs reported prior to first dose of study treatment that increase in severity or frequency after first dose of study treatment through 4 weeks after the final dose of the study treatment or subject's participation

	
Removed redundant language for treatment-emergent adverse events.
 
Clarified final list for adverse events of interest.
 
Specified that deaths would be evaluated.

Sponsor: Bristol-Myers Squibb

Protocol no: IM011046

	
<del>in the study if the last scheduled visit occurs at a later time.</del>
 
 
○ Treatment-emergent adverse events of interest (AEIs) <del>as determined through the Clinical Safety Program (CSP)</del> for the following events:           
 
▪ Skin-related AEs
 
▪ Infection AEs, including influenza
 
▪ Creatine kinase (CK) elevation (evaluated as lab toxicity grade 2 or higher)
 
▪ Malignancy
 
▪ Deaths
 
 
 
○ Laboratory abnormalities (as determined by Common Terminology Criteria for Adverse Events [CTCAE v5.0] grading) presented as the worst postbaseline toxicity group
 
○ Shifts from baseline to maximum postbaseline value
 
○ ALT or AST elevation >5 times ULN
 
 
<math>\geq 500</math> msec
 
Males: < 450 msec, <math>\geq 450</math> msec
 
Females: < 470 msec, <math>\geq 470</math> msec
 
In cases where the QT interval is corrected using Bazett's (QTcB) formula is captured instead of QTcF, then QTcB will be converted to QTcF for analyses.
 
 
• Eight-Item Patient Health Questionnaire (PHQ-8) total score           
 
○ Absolute and change from baseline values
 
○ Shifts from baseline scores
 
○ PHQ-8 total scores <math>\geq 15</math>
 
 
 
○ Electronic Columbia-Suicide Severity Rating Scale (eC-SSRS)           
 
⊖ <del>eC-SSRS items</del> Suicidal ideation and suicidal behavior responses by visit
 
⊖ Shifts from baseline to postbaseline value for suicidal ideation and suicidal behavior
 
⊖ Worst postbaseline value for suicidal ideation and behavior through Week 16
 
 
 
	
Version number added for CTCAE.
 
Provided additional clarifications for lab summaries.
 
Added missing msec for ECG category, new categories for ECG by males and females, and clarification that QTcB will be converted to QTcF for analysis.
 
Removed PHQ-8 total scores <math>\geq 15</math> as this is provided in the shift table.
 
Clarified the variables for eC-SSRS to be summarized.

5.0 Populations for Analysis	Full Analysis Set (FAS): All subjects who are randomized - subjects who are assigned study treatment.	The definition for the Full Analysis Set

Sponsor: Bristol-Myers Squibb

Protocol no: IM011046

	
Per Protocol Set (PPS): A subset of the FAS who are compliant with study treatment and who do not have any <del>statistically</del>-relevant protocol deviations that may impact the coprimary efficacy endpoint assessments.
	
was modified to clarify that the population includes all randomized subjects. Removed “statistically” from relevant deviations in the PPS description to align with standard naming.

5.1 Relevant Protocol Deviations	
Relevant protocol deviations are deviations that can have an impact on the primary efficacy endpoints. The impact of relevant protocol deviations on the primary efficacy results will be assessed by excluding subjects from the FAS to define the PPS in supportive analyses of the primary efficacy endpoints. Relevant protocol deviations to be considered regarding exclusion of subjects from the FAS will include the following:
 
 
• Randomized but did not take any study treatment
 
• No postbaseline PASI or sPGA
 
• Baseline BSA involvement < 10%
 
• Baseline PASI score < 12
 
• Baseline sPGA < 3
 
• Did not have non-plaque psoriasis at baseline
 
• <del>Failed to meet study inclusion criteria but were entered into the study:</del>
 
• <del>Met study exclusion criteria but were entered into the study: (only exclusion criteria expected to have an impact on the primary efficacy endpoints will be considered relevant)</del>
 
• Poor compliance to study medication within the first 16 weeks of treatment defined as <80% compliant with study
 
• Failure to adhere to prohibited concomitant medication restrictions as described below: 
 
○ Investigational drug or placebo taken outside of the study any time between Day 1 and the Week 16 assessment
 
○ Phototherapy within 4 weeks prior to the Week 16 assessment
 
○ Biologic medications (eg, adalimumab, etanercept, infliximab, ustekinumab) any time between Day 1 and the Week 16 assessment
 
○ Oral psoriasis medications any time between Day 1 and the Week 16 assessment
 
○ Oral corticosteroids (unless for the treatment of an adverse event) within 4 weeks prior to the Week 16 assessment
 
 
 
	
Deviations were updated with final categories.

Sponsor: Bristol-Myers Squibb

Protocol no: IM011046

	
 
○ Topical medications/treatments that could affect psoriasis evaluations within 2 weeks prior to the Week 16 assessment
 
○ Medicated shampoos within 2 weeks prior to the Week 16 assessment
 
● <del>Subject overdosed, misused or abused study treatment prior to Week 16</del>
 
● <del>Actual treatment received is different than randomized treatment</del>Subject received treatment that was different than intended treatment at any visit prior to Week 16.
 
 
All subjects with relevant protocol deviations will be identified prior to database lock and unblinding of treatment assignment with the exception of subjects where actual treatment received is different than randomized treatment which will be determined after treatment unblinding. Relevant protocol deviations will be summarized by treatment group and deviation category for the FAS population.
 
<del>Additionally, all important protocol deviations, which are deviations that may impact the efficacy and safety of subjects, will be identified prior to database lock and unblinding of treatment assignment. Important protocol deviations will be summarized by treatment group and deviation category for the FAS population.</del>
	
6.1 Efficacy Analyses	
Coprimary and key secondary efficacy endpoints will be displayed graphically by treatment group and visit, as applicable. <del>Binary endpoints will be displayed using bar charts and continuous endpoints will be displayed using line plots.</del> All efficacy endpoints will be summarized descriptively.
 
The key secondary endpoints will be tested with a two-sided with a significance level of 0.025 to compare BMS-986165 6mg QD vs. placebo and vs. apremilast <del>(equivalent to 0.05 level of significance)</del>. A hierarchical testing approach will be used <del>in for</del> testing of key secondary endpoints <del>(see Section 6.1.3)</del> within each comparison branch. Two-sided 95% confidence intervals (CIs) will be provided for all efficacy estimates. [REDACTED]
 
[REDACTED]
 
<del>The analyses of the primary and secondary endpoints of all subjects including those from Japan and China will include baseline body weight as a factor in the model. Therefore, although the subjects coming from Japan and China may not be balanced by the body weight groups (<90 kg or ≥90 kg), analyses of the endpoints will be adjusted for any effect of the baseline body weight on efficacy. Due to small sample sizes in China and Japan and differences in stratification factors, analyses will be stratified by a combination of the stratification factors used in randomization. The stratified levels are provided below:</del>
 
 
▪ US/PRIOR USE/< 90 KG
 
▪ US/PRIOR USE/≥90 KG
 
▪ US/NAÏVE/<90 KG
 
▪ US/NAÏVE/≥90 KG
 
	
Removed plot description to allow flexibility in data presentation plan.
 
Clarified the language for testing of secondary endpoints.
 
Updated the stratification levels to a combination stratification factor due to small sample sizes in China and Japan.

Sponsor: Bristol-Myers Squibb

Protocol no: IM011046

	
 
▪ ROW/PRIOR USE/< 90 KG
 
▪ ROW/PRIOR USE/≥90 KG
 
▪ ROW/NAÏVE/<90 KG
 
▪ ROW/NAÏVE/≥90 KG
 
▪ JAPAN/PRIOR USE
 
▪ JAPAN/NAÏVE
 
▪ CHINA/PRIOR USE
 
▪ CHINA/NAÏVE
 
 
If there is not at least one subject per treatment group in each of the China and Japan strata, then these regions will be collapsed together to form the following stratified levels for analyses:
 
 
▪ US/PRIOR USE/< 90 KG
 
▪ US/PRIOR USE/≥90 KG
 
▪ US/NAÏVE/<90 KG
 
▪ US/NAÏVE/≥90 KG
 
▪ ROW/PRIOR USE/< 90 KG
 
▪ ROW/PRIOR USE/≥90 KG
 
▪ ROW/NAÏVE/<90 KG
 
▪ ROW/NAÏVE/≥90 KG
 
▪ ASIA/PRIOR USE
 
▪ ASIA/NAÏVE
 
	

6.1.1 Primary Endpoints
 
6.1.1.1 Primary Analysis
	
Analysis Model
 
A stratified Cochran-Mantel-Haenszel (CMH) test will be used to compare the sPGA 0/1 response rates at Week 16 between BMS-986165 6 mg QD and placebo using the stratification factors from IRT specified in Section 6.1. The following prognostic factors are included in the model: geographic region (U.S., Japan, China, Rest of World), body weight (<90 kg, ≥90 kg) and prior biologic use (yes/no). The odds ratio (ratio of odds in BMS-986165 6 mg QD group to the odds in the placebo group) and the corresponding 2-sided 95% CIs and p-values will be reported. Additionally, treatment differences in proportions and the 95% CI for the treatment difference will be provided. The common treatment difference in proportion with the confidence interval, common odds ratio with the confidence interval and p-value will be estimated by the Mantel-Haenszel method consistently.
 
A similar analysis will be performed to compare the PASI 75 response rates at Week 16 between BMS-986165 6mg QD and placebo.
 
Imputation Methodology
 
Non-responder imputation (NRI) will be used for coprimary efficacy endpoints for subjects who:
 
 
• Discontinue treatment or study prior to Week 16
 
	
Clarified stratification to be used and removed prohibited medication criteria.

Sponsor: Bristol-Myers Squibb

Protocol no: IM011046

	
 
Start a protocol prohibited medication/therapy that could improve psoriasis during the first 16 weeks of treatment, or
 
Have missing Week 16 endpoint data for any reason
 
 
Subjects taking protocol prohibited medications during the first 16 weeks of treatment will be identified prior to database lock and treatment unblinding. NRI will be used as the primary method of imputation for the coprimary efficacy endpoints.
	
